12.3 Reporting Adverse Events

Note: The reporting of adverse events for the Cycle 1 portion of the study, i.e., the survey at chemotherapy cycle 1 is described in Section 11 above.

All adverse events, whether observed by study staff or investigator, elicited from or volunteered by the participant, should be documented. Each adverse event will include the date of onset, date of resolution, severity, and the relationship to the **study agent or intervention**, and any action taken with respect to the **study agent or intervention**.

Adverse events will be reported to the URCC NCORP Research Base using REDCap. The following table will be utilized to report adverse events:

Adverse Event – for Cycle 2 portion of the study					
	Grade 1	Grade 2	Grade 3	Grade 4	Grade 5
Unrelated			URCC	URCC	URCC
Unlikely			URCC	URCC	URCC
Possible	URCC	URCC	URCC	URCC	URCC
Probable	URCC	URCC	URCC	URCC	URCC
Definite	URCC	URCC	URCC	URCC	URCC

All adverse events will be reported to the URCC NCORP Research Base on the Adverse Event

Report Form in REDCap. Serious adverse events requiring expedited reporting via CTEP-AERS are described below in Section 12.4. Serious adverse events (described in section 12.2) not requiring expedited reporting through CTEP-AERS should be entered into REDCap within 10 calendar days of learning of the event.

*****Any rash, regardless of attribution should be reported.** See section 8.7.5***

All adverse events reported to the URCC Research Base will be reported to the Data Safety Monitoring Committee.

12.4 Responsibilities for Expedited Reporting

URCC NCORP Research Base affiliates are required to notify the URCC Research Base if a participant has an adverse event requiring expedited reporting. All SAEs that meet expedited reporting criteria defined in the reporting table below will be reported via CTEP-AERS, the Adverse Event Expedited Reporting System, accessed via the CTEP web site, <https://eapps-ctep.nci.nih.gov/ctepaers/pages/task>

Commercial reporting requirements are provided in the table below. The commercial agents used in this study are netupitant/palonosetron, olanzapine, prochlorperazine and dexamethasone.

Expedited reporting requirements for adverse events experienced by participants who have received study agent/intervention within 30 days of the last administration of commercial study agent/intervention should be reported as follow:

Attribution	Grade 4		Grade 5 ^b	
	Unexpected	Expected	Unexpected	Expected
Unrelated or Unlikely			CTEP-AERS ^a	CTEP-AERS ^a
Possible, Probable, Definite	CTEP-AERS ^a	CTEP-AERS ^a	CTEP-AERS ^a	CTEP-AERS ^a

^a Indicates an expedited report is to be submitted via CTEP-AERS within 10 calendar days of learning of the event.

^b This includes all deaths within 30 days of the last dose of study agent with a commercial agent/intervention, regardless of attribution. Any death that occurs more than 30 days after the last dose of study commercial agent/intervention and is attributed (possibly, probably or definitely) to the agent/intervention and is not due to cancer recurrence must be reported according to the instructions above.

Submission of the on-line CTEP-AERS report plus any necessary amendments generally completes the reporting requirements. You may, however, be asked to submit supporting clinical data to the Research Base in order to complete the evaluation of the event.

For more information see:

https://ctep.cancer.gov/protocolDevelopment/electronic_applications/docs/aeguidelines.pdf

Contact Information for NCI Safety Reporting:

Website for submitting expedited reports	http://eapps-ctep.nci.nih.gov/ctepaers
AEMD Help Desk (for CTEP)*	[contact] Monday through Friday, 7:00 AM to 7:00 PM (US Eastern Time)
Fax for expedited report supporting Medical Documentation for CTEP Trials	[contact] (Back-up [contact])
AEMD Help Email:	[contact]

Technical (E.G., IT or computer issues ONLY) Help [contact] or [contact]
CTEP-AERS Technical Help Email	[contact]
CTCAE v 5 Help/Questions Email	[contact]
CTEP-AERS FAQs link	https://ctepcore.nci.nih.gov/ctepaers/help/webhelp/help%20-%20frequently%20asked%20questions.htm
CTEP-AERS Computer based training link	https://ctep.cancer.gov/protocolDevelopment/electronic_applications/adverse_events.htm

Office phone and fax are accessible 24 hours per day 7 days a week (The AEMD phone line is staffed from Monday through Friday, 7:00 AM to 7:00 PM ET. Any phone call after these hours will go to voicemail. Please leave contact information and the phone call will be returned the following business day.)

Additional Instructions:

- Rash, regardless of grade or attribution should be reported.
- All pregnancies occurring in female participants during therapy or within 28 days after completion of treatment on URCC 16070 must be reported via CTEP-AERS using the event term “pregnancy, puerperium and perinatal conditions – other, pregnancy (grade 3).
- CTEP-AERS reports should be amended upon completion of the pregnancy to report pregnancy outcome (e.g., normal, spontaneous abortion, therapeutic abortion, fetal death, congenital abnormalities).
- The CTEP-AERS report should be amended for any neonatal deaths or complications occurring within 28 days of birth independent of attribution. Infant deaths occurring after 28 days considered to be related to in utero to the agent used in this trial should be reported via CTEP-AERS.

13. STUDY MONITORING

13.1 Data Management Summary

This project will collect data in the following formats: paper documents, REDCap electronic questionnaires, and biospecimens (blood).

13.1.1 Paper data are entered electronically at the NCORP site as soon as they are collected by the study coordinator through the secure REDCap system, following the URCC16070 REDCap Manual available on the protocol page of the URCC NCORP Research Base website and processed as follows:

1. Paper data are visually checked by the site coordinator line by line for missing, duplicate, ambiguous or unreasonable responses and if found, they will be corrected prior to electronic data entry.
2. The coordinator will log in to the REDCap system with their uniquely assigned credentials, open the participant's record and enter the data.
3. All paper forms will be uploaded electronically to the URCC NCORP Research Base through REDCap and a copy kept on site.
4. All data entered in REDCap will be double-checked against the corresponding paper form for inconsistencies and checked for missing, ambiguous or unreasonable responses by the research base. If found, the originating site will be queried for such data.
5. One copy of the amended paper form stays on site and an electronic copy must be included in the query response sent to the URCC. Data are amended per GCP on the paper form and in REDCap, and the change is documented at the research base.
6. Queries are also generated if data are not received per the protocol timeline.
7. When all data have been received on any given case, a chart audit is performed at

the research base to ensure receipt and accuracy of all required data.

8. All paper documents are stored in locked file cabinets or in locked, limited access file rooms. The REDCap database of those documents is stored on protected servers located behind University of Rochester firewalls, with limited access.

13.1.2 REDCap data are entered electronically and processed as follows:

1. All REDCap questionnaires are directly filled out electronically by either the participant at home or the coordinator at the site.
2. Data are visually checked in the REDCap system at the URCC NCORP Research Base for ambiguous or unreasonable responses, and if found, the originating site is queried for such data.
3. When a query response is received, REDCap data are amended per GCP, and the change is documented.
4. Queries are also generated if data are not received per the protocol timeline.
5. When all data have been received on any given case, a REDCap database audit is performed to ensure receipt and accuracy of all required data.
6. The REDCap database of those electronic questionnaires is stored on protected servers located behind University of Rochester firewalls, with limited access.

13.1.3 Biospecimens: Blood kits sent from URCC have bar-coded tubes for collecting samples. One kit is used for one data collection time point of one participant. Samples are frozen on site and shipped frozen to URCC on dry ice where they are stored in locked -80° freezers in a research base lab with limited access.

13.2 On-site audits are conducted at least every three years in accordance with NIH/NCI CTMB Guidelines. The primary objective of an on-site audit is to document compliance of the NCORP site with protocol and regulatory requirements, to verify accuracy of data by comparing submitted data to source documents at the NCORP site, and to provide information on good clinical practices in study conduct and data management. The equivalent of 10% of cases accrued at each component site is audited. The on-site pharmacy is also audited at that time.

13.3 Records To Be Kept

SCHEDULE OF DATA COLLECTION			
FORMS	Baseline(Pre-chemotherapy)	After Chemotherapy Cycle 1	After Chemotherapy Cycle 2 for Randomized Participants Only
COMPLETED BY PARTICIPANT			
On-Study Form ¹	X		
Functional Assessment of Cancer Therapy Scale-General (FACT-G) ¹	X	X	X
Medical Symptom Checklist ¹	X	X	X
MASCC Antiemesis Tool (MAT) ¹		X	X
Four-Day Home Record (nausea, vomiting, rescue medication use, fatigue, anxiety, dizziness, and sleep disturbance) ²		X	X
Medication Diary			X
COVID Effects	X		X
COMPLETED BY COORDINATOR			
Consent Form ³	X		
REDCap Participant Information ⁴ (must be completed immediately following registration)	X		
Eligibility Checklist ³	X	X(for Cycle 2)	
Blood Requisition Form ³	X		
REDCap Current Prescription Medications ⁴	X		
REDCap Case Summary Form ⁴	X	X	X
Randomization		X	
Chemotherapy and Supportive Care Records (copy from medical record) ³		X	X
Telephone Contact Sheet ³		X	X
REDCap Adverse Event ⁴	X	X	X
REDCap Investigational Agent Return Form ⁴			X

¹ Paper versions of these forms are available for those participants opting out of using REDCap.

² Paper version only, coordinator will enter data into REDCap at the NCORP site.

³ Paper version only, to be submitted to URCC via scanned PDF or US mail.

⁴ REDCAP version only, no paper version. SAEs will be reported through CTEP-AERs per Section 11 and 12.

13.4 Data and Safety Monitoring Plan

All adverse events reported to URCC are per Sections 11 and 12.

The James P Wilmot Cancer Center Data Safety Monitoring Committee (DSMC) will serve as the DSMC of record for this study. The DSMC provides oversight of study progress and safety by review of accrual and events at regularly scheduled meetings.

Study investigators conduct continuous review of data and patient safety. The Wilmot Cancer Center Peer Review Committee has determined that progress reports of these data will be submitted annually to the DSMC for review. These reports will include: the number of participants enrolled, withdrawals, any significant toxicities, and serious adverse events both expected and unexpected. The research base maintains a database of all adverse events with toxicity grade and information regarding treatment required, complications, or sequelae. A copy of the AE spreadsheet is submitted with the annual progress report to the DSMC for review.

- Any adverse event that is serious, related AND unexpected must be reported within 10 calendar days from notification to the DSMC safety coordinator and DSMC chair. The NCORP sites will report to the URCC NCORP Research Base and if applicable CTEP AERS per Sections 11 and 12 of the protocol. The NCORP Research Base will be responsible for reporting to the DSMC. The DSMC Chair will determine whether further action is required, and when patient safety is of concern, may call an interim meeting.
- Serious adverse events that are related AND expected or unrelated AND unexpected will be reported to the Committee for review at the annual meeting. SAE reports are expected to include sufficient detail so that the DSMC can determine the severity, toxicity grade, expectedness, treatment required, and a follow up report documenting resolution or if there are sequelae. Unless otherwise specified in the protocol, serious adverse events that require reporting (but not necessarily expedited) are expected, related, non-hematologic toxicities of grades 3, 4 or 5. See Sections 11 and 12 for specific reporting requirements for this protocol.

The Data Safety Monitoring Committee provides oversight of study progress and safety by review of accrual and events at regularly scheduled meetings. The DSMC will monitor all adverse event rates utilizing a cumulative spreadsheet listing of events submitted along with progress reports by the PI. All serious adverse events that have occurred in the prior 3 months will be reviewed at the DSMC's regularly scheduled quarterly meeting in order to confirm toxicity grade, expectedness, relatedness, sequelae, follow up required, and risk to current or future subjects.

The URCC will notify the NCORP sites immediately of any serious safety concerns identified by the DSMC. DSMC reports will be available for download on the research base website.

13.5 Record Retention

Clinical records for all participants, including CRFs, all source documentation (containing evidence to study eligibility, history and physical findings, laboratory data, results of consultations, etc.), as well as IRB records and other regulatory documentation will be retained by the Investigator in a secure storage facility in compliance with Health Insurance Portability and Accountability Act (HIPAA), Office of Human Research Protections (OHRP), Food and Drug Administration (FDA) regulations and guidances, and NCI/DCP requirements, unless the standard at the site is more stringent. For NCI/DCP, records will be retained for at least five years after the completion of the research. The records must be accessible for inspection and copying by authorized persons of the Food and Drug Administration and the URCC Research Base.

14. STATISTICAL CONSIDERATIONS

14.1 Study Design/Description

The Cycle 2 portion will be conducted in those participants who experienced moderate or greater nausea at Cycle 1. It will be a Phase III randomized, double-blinded, placebo-controlled clinical trial of an intervention examining the efficacy of the three treatment arms for control of CINV.

14.2 Data Handling

Data will be analyzed as intent-to-treat. The assumptions underlying all statistical analyses will be thoroughly checked using appropriate graphical and numerical methods.(42,43) In the case of serious violations of the assumptions, appropriate nonparametric methods or transformations will be attempted.(44,45) In the event of outlying observations, we will carefully check the data and make corrections if necessary. If no errors are found, we will conduct analyses both with and without the outlying data and report both results to assess the sensitivity. All hypothesis testing will be performed at the two-sided 0.05 level, with the exception of the Primary Analysis, which will use the 0.05/2=0.025 level. SAS, JMP and R will be used for the analyses as appropriate.

14.3 Sample Size and Power

Sample Size: The number of participants needed for the randomized portion of the study will be 111 participants per arm, or 333 total. The accrual necessary at Cycle 1 to have 333 eligible participants for the randomized portion of the trial at Cycle 2 will be 1600. These numbers are derived based upon data from Preliminary Study 2. In that study, 46.1% of the randomized participants reported Peak Nausea of ≥ 3 , the nausea eligibility criterion for this study. Using that number, in order to have 333 eligible participants at Cycle 2, we will need to accrue 724 participants at Cycle 1. We conservatively assume that 10% of the Cycle 1 participants who would be eligible for the randomized portion of the study at Cycle 2 will decide not to continue with the study, so we will increase our targeted accrual at Cycle 1 by 10% to 796 participants. We rounded this number to 800 for our projected recruitment at Cycle 1 and will recruit additional participants beyond the projected 800, if necessary, to reach our Cycle 2 target of 333 randomized participants. In summary, we anticipate approximately 28% of patients screened during Cycle 1 to enroll for the randomized portion of the study. Eligible patients willing to continue on the study, will be immediately following the assessment of CINV after Cycle 1 of chemotherapy randomized to continue on the study. Randomized portion of the study starts at Cycle 2 of chemotherapy. Following URCC Research Base standard operation procedures, data are evaluated for quality immediately upon its receipt. Moreover, the statistical group routinely performs data quality checks to identify problems so corrective action can be taken early. Therefore, we anticipate the data analysis to begin 4-6 weeks after full enrollment is completed and data has matured.

Update 04/29/2020: Based on the first 517 subjects, 214 were eligible for Cycle 2 for 41.4%, falling slightly below of our preliminary estimate of 46.1%. Of the 214 subjects eligible for Cycle 2, only 135 (63%) decided to continue with the study. We had assumed a maximum of 10% would not continue with the study, while in reality 37% of subjects did not continue the study. Therefore, it is necessary to increase our Cycle 1 accrual to 1,200 subjects in order to meet our Cycle 2 target of 333 randomized participants, as the majority of our statistical assumptions are based on that sample size.

Update 08/01/2022: Based on the first 1,084 subjects, 413 were eligible for Cycle 2 for 39.0%, falling slightly below of our preliminary estimate of 41.1%. Of the 413 subjects eligible for Cycle 2, only 241 (58%) decided to continue with the study. We had assumed a maximum of 10% would not continue with the study, while in reality 42% of subjects did not continue the study. Therefore, with recruiting 1500 patients for Cycle 1, it is expected on average (probability 50%) that $=333$ will enroll for Cycle 2. To ensure high probability to reach the targeted goal $n=333$ for Cycle 2, we propose to recruit $n=1600$ for Cycle 1. Recruiting $n=1600$ patients for Cycle 1 provides 90% probability to meet our Cycle 2 target of 333 randomized participants, as the majority of our

statistical assumptions are based on that sample size.

Power: Our target accrual of evaluable participants for the randomized portion of the study is 100 participants per arm. We conservatively assume that 10% of randomized participants will fail to provide evaluable data so we will recruit 111 participants per arm, or 333 total. The standard deviation and pre-post correlation for average nausea at cycle 2 for 35 participants in an ongoing R01 examining acupressure bands in addition to standard antiemetics in breast cancer patients beginning chemotherapy who had nausea of ≥ 3 at cycle 1 and provided data at cycle 2 and did not use acupressure bands were 0.953 and 0.5, respectively.

For the Primary aim, we will use a one-way analysis of variance on Post – Pre change scores. We have Arms 1 (control), 2, and 3. Two tests will be done using contrasts: 1 vs. 2 and 1 vs. 3, and a significance level of $0.05 / 2 = 0.025$. Using the numbers above, we estimate the SD of the change scores to be 0.953, conservatively assuming a pre-post correlation of 0.5. When the sample size in each of the 3 groups is 100, we calculate that our planned one-way analysis of variance will have 90% power to detect a difference in means of 0.48, or a half standard deviation. In light of the fact that there are no minimum clinically important difference (MCID) guidelines for changes in our average nausea measure, this can be considered to be a clinically relevant change.(46)

14.4 Calculation of the Primary Outcome Variable

The primary outcome variable will be Average Nausea (measured on a 7-point scale anchored by “Not at all Nauseated” and “Extremely Nauseated”) defined as the average nausea rating across 15 assessment points (i.e., the afternoon, evening, and night reporting periods on Day 1 and the morning, afternoon, evening, and night reporting periods on Days 2 – 4. In the event that data are missing from eleven or more of the fifteen nausea assessment points, we will set the score to missing.

14.5 Primary Objectives and Analysis Plans

14.5.1 The **Primary Aim** is to determine if control of nausea at Cycle 2 in participants who experienced CINV at Cycle 1 is improved by the addition of either prochlorperazine or olanzapine to the control arm of netupitant, palonosetron and dexamethasone.

14.5.2 **Primary Hypothesis:** Control of nausea at Cycle 2 in participants who experienced CINV at Cycle 1 despite receiving ASCO-recommended antiemetics(1) can be improved by the addition of either prochlorperazine or olanzapine to the standard antiemetic combination of netupitant, palonosetron and dexamethasone.

14.5.3 **Primary Analysis:** We will use a one-way analysis of variance on Post – Pre change scores. We have Arms 1 (control), 2, and 3. Two tests will be done using contrasts: 1 vs. 2 and 1 vs. 3, using a significance level of $0.05 / 2 = 0.025$.

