Screen prior to first chemotherapy: Approximately **1600** breast cancer patients scheduled to receive a chemotherapy regimen that contains doxorubicin, and/or cyclophosphamide, and/or carboplatin provided on a single day and an antiemetic regimen using the antiemetics recommended in the ASCO Clinical Practice Guidelines.

Prior to first chemotherapy: Informed consent, Eligibility Checklist, Participant Information, FACT-G, Medical Symptom Checklist, On-Study Form, Current Prescription Medications, blood draw for biomarker/genetic assessments

First Chemotherapy Cycle

Post-treatment assessments: Four-day Home Record (nausea and vomiting), MASCC Antiemesis Tool (MAT), FACT-G, Medical Symptom Checklist,

If nausea ≥ 3 (on a 1-7 scale)

If nausea < 3 , participant is off study

RANDOMIZED PORTION OF CLINICAL TRIAL

Stratify by NCORP site, vomiting (yes, no), setting (neo-adjuvant, adjuvant or metastatic) and whether participant is receiving a doxorubicin-based chemotherapy

R
a
n
d
o
m
i
z
e

Arm 1

Day 1: One 300mg capsule netupitant/palonosetron approximately 1 hour prior to chemotherapy + dexamethasone 12mg PO 30 minutes prior to chemotherapy + placebo¹ + placebo² q8h
Days 2 - 4: (Dexamethasone 8mg + placebo¹) qam + placebo² q8h

Arm 2

Day 1: One 300mg capsule netupitant/palonosetron approximately 1 hour prior to chemotherapy + dexamethasone 12mg PO 30 minutes prior to chemotherapy + placebo¹ + prochlorperazine 10mg q8h
Days 2 - 4: (Dexamethasone 8mg + placebo¹) qam + prochlorperazine 10mg q8h

Arm 3

Day 1: One 300mg capsule netupitant/palonosetron approximately 1 hour prior to chemotherapy + dexamethasone 12mg PO 30 minutes prior to chemotherapy + olanzapine 10mg + placebo² q8h
Days 2 - 4: (Dexamethasone 8mg + olanzapine) qam 10mg + placebo² q8h

Second Chemo- therapy Cycle

Post-treatment assessments: 4-Day Home Record, MAT, FACT-G, Medical Symptom Checklist

Note: Placebo¹ matches olanzapine and placebo² matches prochlorperazine.

TABLE OF CONTENTS

INSIDE COVER PAGE.....	Error! Bookmark not defined.
SCHEMA	3
1. INTRODUCTION AND BACKGROUND	6
1.1 Rationale	6
1.2 Literature Review and Preliminary Studies	8
1.3 Study Medications	9
1.4 Feasibility.....	9
2. AIMS/OBJECTIVES.....	9
3. CHARACTERISTICS OF STUDY POPULATION	10
3.1 Inclusion Criteria for Participation in the Cycle 1 Portion of the Study.....	10
3.2 Additional Inclusion Criteria for Participants Advancing to the Cycle 2 Portion of the Study.....	11

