3.1.11 Women of child-bearing potential must agree to use adequate contraception (hormonal or barrier method of birth control, or abstinence) for the duration of the study and have a negative pregnancy test within 10 days prior to the initiation of chemotherapy. Should a woman become pregnant or suspect she is pregnant while participating in this study, she should inform her study physician immediately.

3.2 Additional Inclusion Criteria only for the Participants Advancing to the Cycle 2 Portion of the Study

Participants must:

3.2.1 Only participants with a nausea score ≥ 3 at least once on the 4-day home record from Cycle 1 can be randomized for Cycle 2.

3.2.2 Participants must be scheduled to receive the same chemotherapy regimen as received at Cycle 1.

3.2.3 Because quinolone antibiotic therapy can increase the level or effect of olanzapine by altering drug metabolism and thereby potentially increase risk of side effects, patients currently receiving quinolone antibiotic therapy must have approval from an oncologist or their designee to participate in the Cycle 2 portion of the study. (A partial list of quinolone antibiotics is included in the supporting documents section of the protocol webpage.)

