4.4.2 Stratification. The three study arms are stratified by

- NCORP
- Presence of vomiting
- Whether the participant received doxorubicin at Cycle 1
- Chemotherapy setting (neo-adjuvant, adjuvant or metastatic)

4.4.3 Randomization is done exclusively through REDCap. Randomization occurs when both the Four Day Home Record and the Case Summary are entered and marked as complete inREDCap. The following information will be requested:

- NCORP name
- Participant's study ID
- Did the participant report vomiting on the 4-Day Home Record Diary?
- Did the participant receive doxorubicin at Cycle 1?
- Chemotherapy setting (neo-adjuvant, adjuvant, or metastatic)

The three treatment arms for Cycle 2 are:

Arm 1

Agent	Day 1	Day 2	Day 3	Day 4
netupitant/palonosetron	One 300mg capsule approximately one hour prior to chemotherapy			
Dexamethasone	12mg PO 30 minutes prior to chemotherapy	8mg PO in the morning	8mg PO in the morning	8mg PO in the morning
Placebo to match prochlorperazine	One capsule with chemotherapy then q8h	One capsule q8h	One capsule q8h	One capsule q8h
Placebo to match olanzapine	One capsule with chemotherapy	One capsule in the morning	One capsule in the morning	One capsule in the morning

Arm 2

Agent	Day 1	Day 2	Day 3	Day 4
netupitant/palonosetron	One 300mg capsule approximately one hour prior to chemotherapy			
Dexamethasone	12mg PO 30 minutes prior to chemotherapy	8mg PO in the morning	8mg PO in the morning	8mg PO in the morning
Prochlorperazine	10mg PO with chemotherapy then q8h	10mg PO q8h	10mg PO q8h	10mg PO q8h
Placebo to match olanzapine	One capsule with chemotherapy	One capsule in the morning	One capsule in the morning	One capsule in the morning

Arm 3

Agent	Day 1	Day 2	Day 3	Day 4
netupitant/palonosetron	One 300mg capsule approximately one hour prior to chemotherapy			
Dexamethasone	12mg PO 30 minutes prior to chemotherapy	8mg PO in the morning	8mg PO in the morning	8mg PO in the morning
Placebo to match prochlorperazine	One capsule with chemotherapy then q8h	One capsule q8h	One capsule q8h	One capsule q8h
Olanzapine	10mg PO with chemotherapy	10mg PO in the morning	10mg PO in the morning	10mg PO in the morning

5. RESEARCH PROTOCOL/STUDY PROCEDURES**5.1 Summary of Study Plan**

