14.6 Secondary Objectives, Endpoints, Analysis Plans

14.6.1 **Secondary Aim 1** is to determine if olanzapine is more effective than prochlorperazine in controlling nausea at Cycle 2 in participants who experienced CINV at Cycle 1 when used in combination with netupitant, palonosetron and dexamethasone. This will be assessed by estimating the contrast $D = (3 - 1) - (2 - 1)$, where 3 is the Arm 3 mean, 2 is the Arm 2 mean, and 1 is the Control mean, and testing whether $D = 0$ versus the one-sided alternative hypothesis that $D > 0$.

14.6.2 **Secondary Aims 2 and 3** will compare the effects of the interventions on vomiting

by fitting a generalized linear model. The response will be Any Vomiting (yes/no) after Cycle 2, treatment arm as the main factor, and Any Vomiting after Cycle 1 as a covariate. Estimation will be performed using maximum likelihood assuming a binomial distribution and logit link. The same group of contrasts described in the Primary Aim analysis will be estimated and tested, with a significance level of 0.025 to adjust for multiple tests.

14.7 Exploratory Analyses:

14.7.1 We will create an empirically-based algorithm predicting nausea from breast cancer chemotherapy regimens. To do so, we will use the Cycle 1 diary data (total N = approximately 1600 overall) to develop a predictive model for the risk of developing nausea, using age, race, ethnicity, QOL, alcohol consumption, susceptibility to nausea, expectancy, anxiety, level of nausea on the day prior to treatment, and prior history of nausea as potential predictors. For this analysis, the outcome will be binary, with Nausea=YES if Peak Nausea ≥ 3 and NO otherwise. We will apply two modeling paradigms: 1) Classification Trees, and 2) logistic regression.

14.7.1.1 Classification trees consist of finding a series of binary rules with which to base classifications, e.g., if Age is under 65, Race is Caucasian, and highly emetogenic chemotherapy agents are used, there is a X% risk of CINV. These models are very easy to apply in practice and have been shown to be especially effective if there are interactions between the predictors in the model.(47) We will use Conditional Tree methodology for the computations.(48)

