14.7.1.2 Logistic regression will also be performed. This method can be superior to classification trees if there are few, if any, interactions among the predictor variables. The best model will be chosen using leave-one-out cross validation, where an observation is set aside; the model is fit to the remaining ones, and the fitted model is used to predict the set-aside observation. This is repeated for each observation. The resultant set of predictions is compared to the observed data in terms of misclassification rate, sensitivity, specificity and area under the curve.

14.7.2 We will compare the effects of the interventions on QOL, as assessed by the FACT-G, by following the same procedures described under the Primary Aim and the first Secondary Aim, using change in the FACT-G scores as the response.

14.7.3 Descriptive analyses will be conducted on the frequency and severity of side-effects, i.e., sleep disturbance, fatigue, anxiety, and dizziness, across treatment conditions.

14.7.4 Assessment of biological factors (e.g. GSH recycling, genetic markers) may help identify a subgroup of patients at high risk for development of cancer-related or treatment-related side effects, or response to treatment. Assays to investigate these factors may include, for example, measurement of GSH metabolism, assessment of genetic variants such as SNPs, measurement of cytokines, or measurement of proteins associated with drug absorption, distribution, metabolism, and excretion. The most promising assay(s) will be selected at the time of analysis based on the current state of the science.

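### The primary one-way ANOVA leaves out all four stratification factors: still valid, but adding them could gain about 1 power point if they explain 5% of the change score (about 4 at an optimistic 20%)

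*Combined protocol and SAP*

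**What the plan says.** The schema gives the stratification as "Stratify by NCORP site, vomiting (yes, no), setting (neo-adjuvant, adjuvant or metastatic) and whether participant is receiving a doxorubicin-based chemotherapy". Section 4.4.2 ("The three study arms are stratified by") lists the same four factors, and section 4.4.1 sets equal allocation in random blocks of 3 or 6.

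The primary analysis in 14.5.3, repeated in 14.3, is a "one-way analysis of variance on Post – Pre change scores", with contrasts of Arm 1 against Arm 2 and Arm 1 against Arm 3, each at 0.025. One-way means that arm is the only term. Section 14.2 adds no covariates.

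For Secondary Aim 1, section 14.6.1 says "This will be assessed by estimating the contrast" and names no covariates. The FACT-G analysis in 14.7.2 is done "by following the same procedures described under the Primary Aim and the first Secondary Aim". Only the vomiting model in 14.6.2 contains a stratification factor, Cycle 1 vomiting. The plan gives no reason for the difference.

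**The concern.** Stratified blocks partly remove between-stratum differences from the arm contrasts. An arm-only ANOVA still counts those differences as error. If the factors predict the change in nausea, the standard error is somewhat too large and the test tends to be mildly conservative; if they do not, nothing is lost.

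At stake is the precision of the two primary contrasts, not bias or type I error. The factors are already recorded for every randomised participant, so any gain needs no new data. The point concerns the change-score model only.

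**Working it through.** **Inputs from the plan.** 14.3: 100 evaluable per arm, SD 0.953, difference 0.48, "conservatively assuming a pre-post correlation of 0.5". 14.2: two-sided alpha of 0.025 for each primary contrast.

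**The plan's own figure.** SD of change = √(2 × 0.953² × (1 − 0.5)) = 0.953. SE of a contrast = 0.953 × √(2/100) = 0.1348. Noncentrality = 0.48 / 0.1348 = 3.56. The noncentral t on 297 df gives power 0.904 (normal approximation 0.907). The claim of "90% power to detect a difference in means of 0.48, or a half standard deviation" is therefore reproduced.

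**Upper bound on adjusted power.** If the factors explain a share R² of the change-score variance and the arms are fully balanced, the residual SD is 0.953 × √(1 − R²). Power becomes 0.919, 0.933 and 0.958 at R² = 5%, 10% and 20%. These figures should not simply be set against 0.904, because stratification already helps the unadjusted test. Under perfect balance that test has power of about 0.912, 0.918 and 0.930 (normal approximation), with true alpha of about 0.021, 0.018 and 0.012.

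**Range for R².** The documents give none. Suppose the factors explain 20% of Cycle 1 variance and a share k of their effect persists to Cycle 2. With equal SDs and correlation 0.5, change-score R² = 0.20 × (1 − k)². This gives 5% at k = 0.5, 10% at k = 0.293 and 20% at k = 0. Section 3.2.2 ("Participants must be scheduled to receive the same chemotherapy regimen as received at Cycle 1") makes persistence likely, so the low end is plausible and 20% is optimistic.

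**Simulation.** 20,000 trials per setting, averaged over the two contrasts. 333 participants were randomised in blocks of 3 or 6 within NCORP × vomiting × doxorubicin × setting, and 33 were dropped at random. Assumed: 15 or 30 NCORPs of unequal (Dirichlet) size; 30% vomiting; 50% doxorubicin; setting 45/50/5%; factor variance split 40% vomiting, 20% doxorubicin, 10% setting and 30% NCORP. The adjusted model has the three clinical factors as fixed effects and a random NCORP intercept (REML, Kenward-Roger). Monte Carlo SE is about 0.002 for power and 0.001 for alpha.

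| NCORPs | R² | ANOVA power | Adjusted power | Interval half-width, ANOVA ÷ adjusted | ANOVA alpha |
|---|---|---|---|---|---|
| 15 | 0 | 0.905 | 0.904 | 0.998 | 0.0245 |
| 15 | 5% | 0.907 | 0.915 | 1.019 | 0.0213 |
| 15 | 10% | 0.910 | 0.928 | 1.045 | 0.0206 |
| 15 | 20% | 0.913 | 0.950 | 1.104 | 0.0175 |
| 30 | 0 | 0.903 | 0.901 | 0.997 | 0.0251 |
| 30 | 5% | 0.904 | 0.912 | 1.017 | 0.0254 |
| 30 | 10% | 0.907 | 0.925 | 1.041 | 0.0220 |
| 30 | 20% | 0.909 | 0.950 | 1.097 | 0.0202 |

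The adjusted model's alpha is 0.023 to 0.027. The three clinical factors without NCORP give most of the gain: 0.914 and 0.910 at R² 5%, and 0.942 and 0.942 at 20% (15 and 30 NCORPs).

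**NCORP as fixed effects.** This can lose power. With 30 NCORPs (10,000 trials), power is 0.876 at R² 0 and 0.894 at 5%, against 0.903 and 0.905 for the ANOVA in the same runs. A separate simulation, with the four factors weighted equally and NCORP fixed, gave +0.2 to +0.9 points at 5% and +3.3 to +3.5 at 20% with 5 to 20 sites, but −2.3 and +2.2 with 40 sites.

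**With Cycle 1 average nausea in the model.** At r = 0.5 the residual variance falls to 1 − 0.5² = 0.75 of its former value, and power is already about 0.968. Adding the strata then changes it by only −0.2 to +0.8 points: for example, 0.968 to 0.966 where the change-score R² is 5%, and 0.969 to 0.975 where it is 20% (15 NCORPs).

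**The case against.** The strongest reply is that nothing here is an error. The ANOVA is prespecified, unbiased and powered as planned, and no section promises an adjusted analysis. That stands.

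The size of the gain rests on assumed R², site numbers and factor prevalences. A change-score R² of 20% needs factors that explain 20% of Cycle 1 nausea and nothing at Cycle 2, which is hard to square with 3.2.2. If 80% of such an effect persists, R² is 0.20 × 0.2² = 0.8%; with full persistence it is zero. This also stands, and is why the low end deserves most weight.

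Conservatism is not visible everywhere. At R² 5% with 30 NCORPs the ANOVA alpha is 0.0254. There are 30 × 2 × 2 × 3 = 360 cells for 333 participants, so most blocks are incomplete. The figure is within Monte Carlo error of 0.025, but mild conservatism should be read as a tendency.

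Cycle 1 average nausea would gain far more than the strata, about 6 points. That is correct and limits the value of this change, but it does not make adjusting for the strata unsound. Finally, the random NCORP intercept adds little at R² 5% (0.914 to 0.915, and 0.910 to 0.912). Its purpose is to represent the design without the loss that fixed site effects can cause.

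**Conclusion.** The point holds as a minor efficiency improvement. All four stratification factors are missing from the primary model, without explanation. The planned test remains valid and meets its 90% power.

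Adjusting gains about 0.8 points if the factors explain 5% of the change score, 1.8 at 10%, and about 4 (3.7 to 4.1) at an optimistic 20%. Unadjusted intervals are then about 2%, 4–5% and 10% wider. If the factors explain nothing, adjusting costs 0.1 to 0.2 points. These figures depend on the assumed R², NCORP numbers and factor prevalences, none of which the documents give. Confidence in the size is medium; the omission itself is plain from the text.

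**What to change.** In 14.5.3, specify a linear mixed model (REML, Kenward-Roger degrees of freedom) for the change score. Enter arm, Cycle 1 vomiting (yes/no), doxorubicin (yes/no) and setting (three levels) as fixed main effects, and NCORP as a random intercept. Test 1 vs 2 and 1 vs 3 at 0.025. Do not enter NCORP as fixed effects. Keep the one-way ANOVA as a sensitivity analysis, and use the same model for the contrast in 14.6.1; 14.7.2 then follows. The vomiting model in 14.6.2 needs no change.

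If the sponsor prefers the plain ANOVA, one sentence is enough: the strata are omitted on purpose and the test may be slightly conservative. If Cycle 1 average nausea is to be a covariate, settle that first, because little then depends on the strata.

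The statistical cost is four fixed-effect degrees of freedom. No new data are needed, since the factors are entered in REDCap at randomisation (4.4.3). The administrative cost is a protocol amendment through DCP and the CIRB (15.1), to be made before unblinding. No interim analysis is planned (14.8). The documents do not give the trial's present status; by the August 2022 update in 14.3, 241 participants had continued to Cycle 2. The sponsor may reasonably judge the gain too small for an amendment of its own.
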